This amendment will allow participants with COVID-19 to enroll in Part 3 (treatment only) of Study PYAD who have recovered from prior COVID-19 infection, or have received prior administration of convalescent plasma, monoclonal antibody, or vaccine for SARS-CoV-2. Inclusion will allow for collection of data to explore safety of treatment of LY3819253 alone or in combination with LY3832479 in any of these participant populations.

Section # and Name	Description of Change	Brief Rationale
Section 1.3.1 Part 1 and Prevention Cohort of Part 2	Updated “Prior treatments of special interest” to collect prior use of SARS-CoV-2 vaccine.	The SARS-CoV-2 vaccine is now allowed.
Section 1.3.2 Part 2 Treatment Cohort and Part 3		
2.2 Background	Added background on PYAB interim results.	Emerging data.
2.3 Benefit/Risk Assessment	Updated risk information for LY3819253.	Emerging data.
4.2 Scientific Rationale for Study Design	Added rationale for participants who have received the SARS-CoV-2 vaccine. Added language for Part 3 to reflect that participants who were in independent living situations at the facilities could be enrolled.	Vaccines are now available to the public and those who received a vaccine are allowed in the study. Clarification.
5.2 Exclusion Criteria	Updated Criteria 7, 8, 9, 11, 12, and 13.	This amendment will allow participants with COVID-19 to enroll in Part 3 (treatment only) of the study having recovered from prior COVID-19 infection, or having received prior administration of convalescent plasma, monoclonal antibody, or vaccine for COVID-19. Inclusion will allow for collection of data to explore safety of treatment of LY3819253 alone or in combination with LY3832479 in any of these participant populations.

Section # and Name	Description of Change	Brief Rationale
6.3 Measures to Minimize Bias: Randomization and Blinding	Added stratification factor for whether a participant received a vaccine or not prior to screening	The SARS-CoV-2 vaccine is now allowed
11 References	Added Chen et al. 2020 reference	Source for information in Section 2.3

Table of Contents

1. Protocol Summary	8
1.1. Synopsis	8
1.2. Schema	15
1.3. Schedule of Activities (SoA)	17
1.3.1. Part 1 and Prevention Cohort of Part 2	17
1.3.2. Part 2 Treatment Cohort and Part 3	24
2. Introduction	28
2.1. Study Rationale	28
2.2. Background	28
2.3. Benefit/Risk Assessment	29
3. Objectives and Endpoints.....	31
4. Study Design	37
4.1. Overall Design	37
4.1.1. Screening Period	37

1.1. Synopsis

Protocol Title: A Phase 3 Randomized, Double-Blind, Placebo-Controlled Trial to Evaluate the Efficacy and Safety of LY3819253 alone and in combination with LY3832479 in Preventing SARS-CoV-2 infection and COVID-19 in Skilled Nursing and Assisted Living Facility Residents and Staff; a NIAID and Lilly Collaborative Study

Short Title: A Study to Evaluate LY3819253 alone and in combination with LY3832479 for the Prevention of SARS-CoV-2 infection and COVID-19; a NIAID and Lilly Collaborative Study

Rationale:

The efficient community spread of SARS-CoV-2 has resulted in the current pandemic of Coronavirus Disease – 2019 (COVID-19), which in severe and critical cases results in progressive pulmonary infection, complicated by respiratory failure, with a high prevalence of acute respiratory distress syndrome. Of all age groups, older adults have the greatest risk of severe COVID-19 and the associated complications (CDC 2020; Grabowski and Mor 2020).

Globally, there are many reports of the rapid spread of COVID-19 amongst residents of skilled nursing facilities following identification of an index case, with high associated rates of morbidity and mortality (Arons et al. 2020; Grabowski and Mor 2020; Graham et al. 2020). In the USA, at least 153,000 residents and employees of nursing homes have contracted COVID-19, accounting for 35% of the country's deaths (Werner et al. 2020). With over 1.3 million residents in nursing home care in the USA (CDC 2016), there is an urgent need for therapeutic strategies to prevent COVID-19 in these populations.

This study aims to evaluate the impact of LY3819253 alone and in combination with LY3832479 in preventing SARS-CoV-2 infection and COVID-19 in facility staff and residents in skilled nursing and assisted living facilities with a high risk of SARS-CoV-2 exposure.

Objectives and Endpoints**Part 1**

To facilitate rapid prophylaxis and treatment of residents and facility staff, participants will be enrolled prior to assessment of baseline SARS-CoV-2 reverse transcription – polymerase chain reaction (RT-PCR) or serology results; thus, multiple analysis populations will exist. This includes separate prevention and treatment analysis populations (defined in the tables below) and baseline serology positive participants. Exploratory endpoints, including the treatment analysis population, are described in Section 3.

Safety, pharmacokinetics, and antidrug antibodies will be characterized in the overall intent to treat population and in the analysis populations.

Additional population subset analyses are detailed in Section 9 and/or in the statistical analysis plan.

Prevention Population Objectives and Endpoints	
Participants negative at baseline for SARS-CoV-2 RT-PCR and serology	
Comparison Groups: Placebo vs LY3819253 4200 mg	
Objectives	Endpoints
Primary	

Compare the incidence of COVID-19	
Cumulative incidence of COVID-19 defined as the detection of SARS-CoV-2 by RT-PCR AND mild or worse disease severity^a within 21 days of detection
Time frame for endpoint evaluation: 8 weeks from randomization
Key Secondary	

Compare the incidence of moderate or worse severity COVID-19	
Cumulative incidence of moderate or worse severity COVID-19; defined as the detection of SARS-CoV-2 by RT-PCR AND moderate or worse disease severity^a within 21 days of detection
Time frame for endpoint evaluation: 8 weeks from randomization

Compare the incidence of SARS-CoV-2 infection	
Cumulative incidence of SARS-CoV-2; defined as the detection of SARS-CoV-2 by RT-PCR
Time frame for endpoint evaluation: 4 weeks from randomization

Other Secondary	
[time frame for endpoint evaluation: 8 weeks from randomization]	
• Compare the incidence of SARS-CoV-2 infection	• Cumulative incidence of SARS-CoV-2 infection defined as the detection of SARS-CoV-2 by RT-PCR
• Compare the frequency of hospitalization or death due to COVID-19	• Proportion of participants who are hospitalized or have died due to COVID-19
• Characterize clinical status for participants.	• Proportion (percentage) of participants who experience these events: ○ COVID-19 related hospitalization (defined as ≥ 24 hours of acute care), ○ COVID-19 related emergency room visit, or ○ death
• Compare the mortality due to COVID-19	• Proportion of participants who die due to COVID-19 (according to the investigator)

Abbreviations: COVID-19 = coronavirus disease – 2019; RT-PCR = reverse transcription – polymerase chain reaction; SARS-CoV-2 = severe acute respiratory syndrome coronavirus 2.

^a As defined in [Table 1](#).

Part 2 Prevention

Participants will be tested with point of care SARS-CoV-2 POC test to determine SARS-CoV-2 status. Participants with a negative POC test will randomize to the Prevention Cohort. Those with a positive test will enroll to the Treatment Cohort.

Safety, pharmacokinetics, and antidrug antibodies will be characterized in the overall intent to treat population and in the analysis populations.

Additional population subset analyses are detailed in Section 9 and/or in the statistical analysis plan.

Part 2 Prevention Population Objectives and Endpoints
 
Participant negative on screening Point of Care Test
 
&
 
negative at baseline for SARS-CoV-2 RT-PCR and serology
 
Comparison Groups:
 
 • Placebo vs LY3819253 700 mg • Placebo vs LY3819253 350 mg + LY3832479 700 mg 	
Objectives	Endpoints
Primary	

 • Compare the incidence of COVID-19 	
 • Cumulative incidence of COVID-19 defined as the detection of SARS-CoV-2 by RT-PCR AND mild or worse disease severity^a within 21 days of detection 
 • Time frame for endpoint evaluation: 8 weeks from randomization
Key Secondary	

 • Compare the incidence of moderate or worse severity COVID-19 	
 • Cumulative incidence of moderate or worse severity COVID-19; defined as the detection of SARS-CoV-2 by RT-PCR AND moderate or worse disease severity^a within 21 days of detection 
 • Time frame for endpoint evaluation: 8 weeks from randomization

 • Compare the incidence of SARS-CoV-2 infection 	
 • Cumulative incidence of SARS-CoV-2; defined as the detection of SARS-CoV-2 by RT-PCR, 
 • Time frame for endpoint evaluation: 4 weeks from randomization

Other Secondary	

Characterize the pharmacokinetics of LY3819253 and LY3819253 in combination with LY3832479	
Mean concentration of LY3819253 and LY3819253 in the presence of LY3832479 on Day 29Mean concentration of LY3832479 in the presence of LY3819253 on Day 29

Abbreviations: COVID-19 = coronavirus disease – 2019; RT-PCR = reverse transcription – polymerase chain reaction; SARS-CoV-2 = severe acute respiratory syndrome coronavirus 2.

^a As defined in [Table 1](#).

Part 3 objectives are exploratory and therefore described in [Section 3](#).

Overall Design

Study J2X-MC-PYAD is a randomized, double-blind, placebo-controlled, prophylaxis study to evaluate the efficacy and safety of intravenous LY3819253, alone and in combination with LY3832479, in preventing SARS-CoV-2 infection and COVID-19, compared to placebo. An independent Data Safety Monitor Board (DSMB) will actively monitor interim data to make recommendations about early study closure or changes to sample size.

Disclosure Statement: This is a three-part, 9-arm interventional study that is double-blinded.

Number of Participants:

For Part 1, a total of approximately 1700 participants (intent-to-treat [ITT] population) will be randomly assigned to study intervention such that approximately 1300 SARS-CoV-2 RT-PCR and serology negative participants are randomized in the study with the goal of achieving approximately 33 events (in each of the primary and key secondary endpoints) in the prevention population.

For Part 2, a total of approximately 2000 participants will be randomly assigned to study intervention based on rapid point of care (POC) testing such that approximately 1700 participants SARS-CoV-2 RT-PCR and serology negative participants are randomized in the Prevention Cohort with the goal of achieving approximately 56 events on each of the primary and key secondary endpoints.

Part 3 will enroll at least 30 participants and up to approximately 500 participants randomized to study intervention.

The maximum sample size for this study is approximately 5000 participants in the ITT population.

Intervention Groups and Duration:

Participants will receive one intravenous infusion of study intervention.

The maximum total duration of study participation for each participant of the prevention groups is 24 weeks.

The maximum total duration of study participation for each participant of the treatment group is 12 weeks.

Part 1:

Eligible participants will be randomized to one of two arms: placebo or LY3819253 4200 mg.

Participants will continue to enroll to Part 1 until the needed events for the primary and key secondary endpoints are achieved and the minimum number of residents enroll.

The evaluation period for Part 1 is 8 weeks, with follow-up to 24 weeks.

Part 2:

The Sponsor will decide when to trigger activation of Part 2. Activation of Part 2 will be communicated to sites.

All participants will be screened for SARS CoV-2 with a point of care (POC) test. Participants who are negative will be assigned to the “Prevention Cohort”, while those who test positive will be assigned to the “Treatment Cohort”.

- Prevention Cohort: Participants who are SARS-CoV-2 negative during screening on the POC test will be randomized to one of three arms: placebo, LY3819253 700 mg, or LY3819253-350 mg + LY3832479-700 mg.

If enrolling to a placebo-controlled trial is challenged by an effective medication becoming available for prevention of COVID-19 and SARS-CoV-2, then the placebo arm may be dropped.

Note: It is possible that some participants have SARS-CoV-2 negative result on the screening point of care test, but could be positive on the baseline SARS-CoV-2 PCR test. The results from the baseline test will not be available until after the participant is randomized. Once positive results are known from the baseline test, these participants will be unblinded and have the option to continue to be followed for safety according to the Prevention Cohort SoA. Unblinded participants will not be included as part of the defined prevention population.

The evaluation period for the Prevention Cohort is 8 weeks, with follow-up to Day 169.

- Treatment Cohort: Participants who test SARS-CoV-2 positive during screening with the POC test will be randomized to one of two arms: LY3819253 700 mg, or LY3819253 700 mg + LY3832479 1400 mg.

The evaluation period for the Treatment Cohort is 4 weeks, with follow-up to Day 85.

Part 3

[figure not shown]
The Sponsor will decide when to trigger activation of Part 3. Activation of Part 3 will be communicated to sites. Part 3 may be activated prior to Part 2.

Eligible participants will be randomized to one of two arms: LY3819253 700 mg or LY3819253 700 mg + LY3832479 1400 mg. The evaluation period for Part 3 is 4 weeks, with follow-up to Day 85.

Data Monitoring Committee: Yes. Equivalent to Data Safety Monitoring Board for this study.

[figure not shown]

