9.2. Sample Size Determination

For Part 1, an estimated 33 events are needed to show superiority of LY3819253 4200 mg over placebo in each of the primary and key secondary endpoints, using the formula by Schoenfeld (1983). An average sample size of approximately 1300 participants who are SARS-CoV-2 PCR negative and serology negative at baseline is expected to obtain the needed number of events for each endpoint.

For Part 2, an estimated 56 events in the Prevention Cohort are needed to show superiority over placebo for either LY3819253 700 mg or LY3819253 350 mg+LY3832479 700 mg in each of the primary and key secondary endpoints. Approximately 2000 participants on average will be randomly assigned to study intervention such that approximately 1700 participants are randomized in the Prevention Cohort with the goal of achieving approximately 56 events on each of the primary and key secondary endpoints.

Due to the dynamic nature of the pandemic, Part 3 will enroll at least 30 participants and up to approximately 500 participants randomized to either LY3819253 700 mg or LY3819253 700 mg + LY3832479 1400 mg. Part 3 of the study is considered exploratory and is not powered for inference between the two treatment arms.

The maximum sample size for this study is approximately 5000 participants in the intent-to-treat (ITT) population.

Participants will be residents and staff of skilled nursing and assisted living facilities. Globally, there are many reports of the rapid spread of COVID-19 amongst residents of skilled nursing facilities following identification of an index case, with high associated rates of morbidity and mortality (Arons et al. 2020; Grabowski). Given that residents at these facilities are at higher risk for having a more severe disease course of COVID-19, this will be an important population to participate in the study. Therefore, a minimum of 300 residents will be enrolled.

Operationally, this will be accomplished, when possible, by identifying facilities where approximately half of the participants interested in the study are residents.

For sample size determination for Part 1, the following assumptions were used:

- 1) two-sided significance level of 0.05;
- 2) 90% power for the primary and key secondary endpoints;
- 3) an 8-week placebo group event rate of 4.0% for moderate or worse severity COVID-19;

4) a risk ratio of 0.33 between LY3819253 and placebo in terms of the primary and key secondary endpoints.

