### **6.1.5. Timing of Primary Analysis**

#### **6.1.5.1. Part 1 Primary Analysis**

To ensure that all primary and key secondary endpoints are well-powered, database lock for the primary and key secondary endpoints in Part 1 (the Part 1 Primary Database Lock) will be triggered when at least 300 facility residents have been enrolled and when 33 participants in the Part 1 Prevention population experience a moderate or worse severity case of COVID-19. All pre-specified analyses will be based on the Primary Database Lock. However, if the accumulation of moderate or worse severity cases of COVID-19 occurs slower than expected, the Primary Database Lock may be triggered when at least 36 participants in the Part 1 Prevention population test positive for SARS-CoV-2 within 4 weeks of randomization. If this is the case, only the primary endpoint will be evaluated at the Primary Database Lock. At the time of the primary analysis for Part 1, only data from patients enrolled in Part 1 will be unblinded to the sponsor.

To account for participants who have not finished the Evaluation Period at the time of the Primary Database Lock, a supplementary database lock (the Part 1 End of Evaluation Database Lock) will occur once all participants have completed the Evaluation Period or discontinued from the study. The analyses conducted during the Primary Database Lock will be re-evaluated at the End of Evaluation Database Lock.

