## 6.10. Efficacy Analyses

### 6.10.1. Primary Outcome and Methodology

The endpoint for the primary analysis is defined as the first occurrence of COVID-19, defined as the detection of SARS-CoV-2 by reverse transcription – polymerase chain reaction (RT-PCR) AND mild or worse disease severity within 21 days of detection, by Day 57 (8 weeks after randomization).

The percentage of patients in the Prevention population who experience COVID-19 by Day 57 will be summarized by treatment group.

Statistical comparison between each study intervention and placebo will be done using a logistic regression model. The model will include treatment, facility, role within the facility (resident vs staff) and sex as fixed effects. The odds ratio and the corresponding CIs, as well as the treatment differences and the corresponding CIs, will be computed using the Wald method and reported. A p-value from the Rao's score test will be reported.

As an exploratory analysis, the incidence of COVID-19 within 21 days of randomization will be compared across treatment groups in the subset of participants in the Treatment population who are asymptomatic at baseline (as defined in Table 1 of the protocol). Statistical comparisons will use similar methodology as described in Section 6.10.1.

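### Part 1: about 33 events give roughly 84–87% power for moderate-or-worse COVID-19 under the planned score test; the stated 90% is the Schoenfeld approximation

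*Protocol*

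**What the plan says.** Protocol 9.2, repeated in SAP 5.2, says that "an estimated 33 events are needed to show superiority of LY3819253 4200 mg over placebo in each of the primary and key secondary endpoints", and names the Schoenfeld (1983) formula as the source. The listed inputs are a "two-sided significance level of 0.05", "90% power for the primary and key secondary endpoints", "an 8-week placebo group event rate of 4.0% for moderate or worse severity COVID-19" and "a risk ratio of 0.33 between LY3819253 and placebo in terms of the primary and key secondary endpoints". About 1300 participants who are PCR-negative and serology-negative at baseline are expected to supply the events. The synopsis sets the Part 1 enrolment "with the goal of achieving approximately 33 events (in each of the primary and key secondary endpoints) in the prevention population" but gives no power figure.

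On the analysis, SAP 6.10.1 states: "Statistical comparison between each study intervention and placebo will be done using a logistic regression model". The p-value comes from Rao's score test, and facility, role and sex are fixed effects. SAP 6.1.5.1 locks Part 1 "when 33 participants in the Part 1 Prevention population experience a moderate or worse severity case of COVID-19", provided that at least 300 residents have been enrolled.

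**The concern.** Schoenfeld's formula is a large-sample approximation. It treats the events as splitting equally between the arms and is accurate when the effect is modest. Here the assumed effect is strong: at a risk ratio of 0.33 about three quarters of the events fall on placebo (0.040/0.0532 = 75%). The total count is also small. Both features raise doubt whether 33 events deliver 90% under the test that will be run.

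The count matters beyond planning because it triggers the database lock, so moderate-or-worse COVID-19 is tested at or near it. If true power is in the mid-80s, a non-significant result on that endpoint would be read against a stronger design than the trial has.

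**Working it through.** **Inputs.** From protocol 9.2: two-sided alpha 0.05, power 90%, placebo rate 4.0%, risk ratio 0.33, 33 events, about 1300 participants. From protocol 6.3: 1:1 allocation, so 650 per arm. Derived: active rate 0.33 × 4.0% = 1.32%; odds ratio (0.0132/0.9868)/(0.04/0.96) = 0.321; hazard ratio ln(0.9868)/ln(0.96) = 0.326. No dropout rate is given and none is used.

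**1. The plan's own figure.** Schoenfeld at 1:1: events = 4(1.960 + 1.282)²/(ln θ)²; power at 33 events = Φ(½√33·|ln θ| − 1.960).

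| θ entered | Events for 90% | Power at 33 |
|---|---|---|
| Odds ratio 0.321 | 32.6 | 90.4% |
| Hazard ratio 0.326 | 33.4 | 89.7% |
| Risk ratio 0.33 | 34.2 | 89.0% |

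The count of 33 is reproduced. Expected events in 1300 participants are 650 × (0.040 + 0.0132) = 34.6, consistent with the planned sample size.

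**2. Score test, two-proportion formula.** With mean rate p = 0.0266, power = Φ{[0.0268√n − 1.960√(2p(1−p))]/√(0.04·0.96 + 0.0132·0.9868)} = Φ{[0.0268√n − 1.960 × 0.2276]/0.2268}.

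- n = 620 per arm (620 × 0.0532 = 33.0 expected events): 83.5%.
- n = 650 per arm (34.6 expected events): 85.2%.

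**3. Score test, exact.** This sums the two binomial distributions over every outcome that the unadjusted score (Pearson) test rejects.

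- 620 per arm: 85.6%.
- 650 per arm: 87.2%, with actual size 0.050.

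**4. Exactly 33 events.** With 650 per arm, 10 active events give a score statistic of 2.29 and 11 give 1.94, so the test rejects in favour of the active arm at 10 or fewer. Under the noncentral hypergeometric distribution with odds ratio 0.321, power is 82.9% and conditional size is 3.3%. Because counts are discrete, both move in a saw-tooth:

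| Events | 32 | 33 | 34 | 35 | 36 | 37 | 38 | 39 | 40 |
|---|---|---|---|---|---|---|---|---|---|
| Power, % | 85.6 | 82.9 | 88.9 | 86.6 | 91.4 | 89.6 | 93.4 | 91.9 | 90.3 |
| Size, % | 4.7 | 3.3 | 5.4 | 3.8 | 6.2 | 4.4 | 6.9 | 5.0 | 3.6 |

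**5. Is the test the cause?** A simulated log-rank test (20,000 runs) gives 85.4% at 620 per arm, 87.2% at 650 per arm, and 82.8% when stopped at the 33rd event. These match the score test, so the optimism lies in the approximation.

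**6. Facility adjustment.** A simulated facility-stratified score test at N = 1300 gives about 86–88%. The number of facilities (25 to 65) and the spread between them are assumptions; the documents give neither.

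**7. What 90% would take.** Exact: about 710 per arm, or 710 × 0.0532 = 37.8 expected events. Two-proportion formula: 756 per arm, or 40.2. The table in step 4 agrees: power stays above 90% from 38 to 40 events, but not at 37.

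**The case against.** The strongest reply is that the plan made no mistake. It names a standard formula, calls the count an estimate, and the formula returns 33 on the odds-ratio scale that the logistic model uses. That stands: a reader might infer an arithmetic error from entering 0.33 directly and getting 34.2, but the documents do not say that 0.33 was used as a hazard ratio, and the difference is about one point of power.

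A reader might also blame the move from a time-to-event formula to a logistic model. Step 5 does not support that, since a log-rank test falls short by the same amount.

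The 82.9% figure could be read as a false-negative risk of about one in six. That overstates the case: 33 is a low point of the saw-tooth, where the test runs at 3.3% and not 5%. The figures that average over event counts are the fair summary.

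The trigger is also a minimum. The 300-resident condition can delay the lock, and the analyses are repeated at the End of Evaluation lock, when more events may have accrued. This softens the consequence but does not make the stated figure correct.

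Finally, nothing shows the primary comparison to be underpowered. Moderate-or-worse cases are a subset of primary-endpoint cases, so the primary endpoint has at least 33 events at that lock and probably more. If a higher placebo rate is assumed for it (10–20%) with 33 events in total, score-test power is about 85–89%; extra events would raise that.

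**Conclusion.** The concern holds as a misstated power figure, not as a wrong event count. On the plan's own inputs, 33 expected events to 1300 participants give 83.5–87.2% for the planned score test at two-sided 0.05, about 3 to 6 points below 90%. The chance of missing the assumed effect is about 13–16% and not 10%.

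This rests on 4.0% versus 1.32%, 1:1 allocation, no dropout and no covariates; facility adjustment changes it little. It applies mainly to moderate-or-worse COVID-19, the only endpoint with a stated rate and the one whose count triggers the lock. The documents do not support extending it to the primary endpoint.

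It is also separate from the alpha split in SAP 6.5, since it exists at the full 0.05. At the first-step level of 0.04 for this endpoint, exact power is 83.6% (620 per arm) to 85.3% (650 per arm).

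**What to change.** In protocol 9.2 and SAP 5.2, restate the Part 1 power for 33 events and about 1300 participants as about 84–87% at two-sided 0.05 and risk ratio 0.33 for the planned score test, and note that 90% is the Schoenfeld approximation. The synopsis needs no edit. The cost is one sentence in two places and a slightly less favourable stated power; no analysis or procedure changes.

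Moving the lock trigger to 36 events is not a sound alternative. Its 91.4% comes with a conditional size of 6.2%, and power drops to 89.6% at 37. The 36 in SAP 6.1.5.1 counts infections within 4 weeks, a different endpoint. A stable 90% at 0.05 would need about 38–40 moderate-or-worse events, which is 5 to 7 more than planned.
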